7.3 Precautions

VM202 must not be used on subjects with severe infection. Women of childbearing potential who are administered with VM202 must be careful to avoid pregnancy.

	than for any other reason; The AE disappears when administration of the investigational product is suspended.
Possibly related	 There is evidence that the investigational product has been administered and the time sequence of the AE onset is reasonable; The AE is caused by the investigational product at the same level as other probable reasons; The AE disappears when administration of the investigational product is suspended (if performed);
Unlikely	 There is evidence that the investigational product has been administered; There are other causes with higher possibility than the investigational product; The administration suspension (if performed) result is negative or ambiguous; The re-administration (if performed) result is negative or ambiguous;
Not related	 The subject has not been administered with the investigational product; The time sequence of the administration and the AE onset is not reasonable; There are other obvious causes for the AE;
Unassessable	 There is insufficient evidence to determine the relationship; Information is insufficient or conflicting to determine, and cannot be supplemented or verified;

7.4.2 Severity of AE

Severity of an AE is categorized according to NCI-CTCAE version5.0. AEs that cannot be categorized by the NCI-CTCAE are assessed by the following five grades:

Table 25 General classification in NCI-CTCAE V5.0

Grade	Description of Severity
1	Mild: No symptoms or mild symptoms; only clinical or diagnostic observations possible; no therapeutic intervention is needed.
2	Moderate: Minimal, local, or non-invasive treatment needed; daily activities, including meal preparation and shopping, are limited.
	Severe: Medically meaningful but is not immediately life-threatening; hospitalization or prolongation of hospitalization; disability; not
3	bedridden but daily activities, such as bathing, putting on or taking off clothes, eating, going to the bathroom, and taking medication, are limited.
4	Life-threatening consequences: immediate treatment is needed.
5	Death: AE related to death

7.4.3 Reporting, collection, and recording of AEs

The principal investigator must educate the sub-investigator and subjects or representatives of the subject about all adverse events that may occur after the administration of the investigational product and educate them to report all reactions that occur after administration.

- All AEs that occur from administration of investigational product to follow-up visits (until end of the clinical trial) are collected. However, if a sign, symptom, or disease that occurred before the administration is worsened after the administration, it shall also be considered an AE.
- An AE must be reported including the name of the AE, start date and end date, severity, actions related to investigational product, progress, causality with the investigational product, remedial treatment, and whether it is an SAE.
- When documenting an AE, the investigator uses a comprehensive diagnosis or symptom name using standard medical terminology instead of each symptom or sign.
- 4) AEs are observed for the study period of nine months (day 0 to 270). If an AE or SAE that occurs within the nine-month follow-up period is not resolved within this period, follow-up shall be conducted until the AE is resolved.

7.4.3.1 Collection, and recording of AESI(Adverse Events of Special Interest)

All AESIs that occur throughout the clinical trial are collected, the following events are classified as AESI, and the Helixmith PV team manages them as safety information data.

- 1) Coronavirus Disease-19 (COVID-19)
- 2) Injection Site Reactions

7.4.4 Reporting and recording of SAEs

7.4.4.1 Reporting of SAEs

The Investigator prepares and submits the "SAE Report Form" through the eCRF system within 24 hours of recognizing any SAEs regardless of causality with the investigational product. When the Investigator's electronic signature and submission are complete, a notification e-mail is sent to Dt&SanoMedics PV team and Helixmith Co., Ltd. If the SAE Report cannot be prepared and submitted through the eCRF system due to unavoidable circumstances, the "SAE Report Form" is prepared and submitted to the safety information contact person below by fax or email:

Safety reporting contact information

Contact

Dt&SanoMedics PV Team

person

[contact] e-mail [contact]

address [name]

The initial SAE Report must include the following four minimal elements of information:

- 1) An identifiable reporter
- 2) An identifiable patient
- 3) A suspect drug
- 4) A serious adverse event

The following are the responsibilities of each person in charge regarding the SAEs occurring during the clinical study period:

1) Principal Investigator

When an SAE occurs, the principal investigator immediately reports it to the Sponsor (within 24 hours of recognizing). When important additional information regarding the SAE is available later, the principal investigator must submit an additional report including details, within 24 hours of recognizing the additional information. Or, in case of a suspected unexpected serious adverse reaction, it must be expeditiously reported to the Sponsor and IRB. When a death case is reported, the principal investigator must provide additional information such as the autopsy report (only if an autopsy was conducted) and death certificate to the Sponsor and IRB.

2) Sub-Investigator(s)

When an SAE occurs, the sub-investigator(s) must immediately report it to the principal investigator and Sponsor and later submit an additional report containing details. Or, in case of a suspected unexpected serious adverse reaction, it must be expeditiously reported to the principal Investigator, Sponsor, and IRB.

3) Institutional Review Board (IRB)

The IRB requires the principal investigator to take necessary actions if there is a suspected unexpected serious adverse reaction or any new information that may negatively affect the safety of subjects or operation of the clinical study.

4) Sponsor

- (1) The Sponsor reports any suspected unexpected serious adverse reactions to other relevant investigators, the IRB (only if the Investigator has not reported them to the IRB or there is a need to change content of the report), and the Ministry of Food and Drug Safety (MFDS) within 15 days of receiving a report from the principal investigator or sub-investigator(s) on or recognizing them. Or, in the event of death or life-threatening, the Sponsor must report on it within seven days of receiving a report on or recognizing it, and report further detailed information within eight days of the initial reporting. When submitting a SUSAR report, information received from the principal investigator or sub-investigator(s) shall be attached.
- (2) The Sponsor must periodically report additional safety information related to the above report until the SUSAR is concluded (the disappearance of the SUSAR or inability to follow up). The investigator must actively cooperate in providing data and information regarding the report.

7.4.4.2 Reporting Suspected Unexpected Serious Adverse Reaction (SUSAR)

The Sponsor has the obligation to continuously conduct assessment on the safety of

the investigational product used in the clinical study.

The Sponsor must expeditiously report any SUSARs to the other relevant investigators, the IRB, and the MFDS within the period specified as follows:

- (1) The Sponsor must expeditiously report any SUSARs to the other relevant investigators, the MFDS, and, when necessary, the IRB within the period specified as follows:
 - A) Death or life-threatening: Within seven days of receiving a report on or recognizing the event. Or, if the initial report lacks any of the information required in the attached Form 77, the ADR Report, including the name of the ADR, final observation result, and ADR summary, an additional report must be submitted with detailed information on the ADR within 15 days of receiving report on or recognizing the event.
 - B) Others: within 15 days of the Sponsor receiving report on or recognizing the event.
- (2) If there is additional information on the adverse drug reaction reported under subsection (1), the Sponsor must report it until the adverse drug reaction is concluded (referring to the disappearance of the ADR or the inability to conduct a follow-up).
- (3) When the Sponsor intends to report the ADR to the Minister of Food and Drug Safety pursuant to subsection (1), an ADR summary, including CIOMS-I form, must be attached to Form 77, the ADR report.

7.4.5 Handling AE

All AEs which occur during the study period must be recorded in detail in the Case Report Form, including symptoms and signs, start date/end date, duration, severity, treatment and results, and causality with the investigational product even if they are not related to the investigational product. In addition, if possible, the AE shall be observed until it is recovered to pre-administration or baseline level, or until the investigator can determine that the AE has been normalized, or until further observation is deemed unnecessary.

Handling of the AE is categorized as follows:

- 1) Drug administration maintained
- 2) Drug administration interrupted
- 3) Drug administration permanently discontinued

- 4) N/A: The subject has deceased, or administration is terminated when the AE occurs
- 5) Unknown

Treatments of the AE are categorized as follows:

- 1) Perform drug treatment of the AE
- 2) Perform non-drug treatment of the AE
- 3) Perform drug/non-drug treatment of the AE
- 4) No drug/non-drug treatment of the AE

Results of the AE are categorized as follows:

- 1) Recovered (resolved)
- 2) Recovering (being resolved)
- 3) Not recovered (not resolved)
- 4) Recovered (resolved) with sequelae
- 5) Death possibly related to the AE
- 6) Death not related to the AE
- 7) Unknown

7.4.6 Handling related to investigational product

During the clinical study, the principal investigator and sub-investigator(s) must make every effort to secure the safety of the subjects and take prompt and appropriate interventions to minimize AEs when SAEs occur. The principal investigator may discontinue the clinical study in consultation with the Sponsor. Even when not related to the investigational product, all AEs that occur during the clinical study period must be recorded in detail in the Case Report Form, with the symptoms and signs, start date/end date of occurrence, duration, severity, treatment and results, and causality with the investigational product. In addition, if possible, cases shall be observed until the AE is recovered to the preadministration or baseline level, or until the investigator can determine that the AE has been normalized, or until further observation is deemed unnecessary.

When an AE occurs, the following interventions shall be taken:

- 1) Dose maintained
- 2) Dose increased
- 3) Dose reduced
- 4) Drug administration interrupted
- 5) Drug administration permanently discontinued

- 6) N/A: The subject has deceased, or administration is terminated when the AE occurs
- 7) Unknown

7.4.7 Pregnancy report

Female subjects of childbearing potential and male subjects who are sexually active with women of childbearing potential must practice appropriate contraception until the 7th visit (last visit, Day 270) after the last administration of the investigational product.

The appropriate contraception methods acknowledged in this clinical study are:

- Hormonal contraceptives
- Insertion of an Intrauterine device or system
- Double barrier method*(spermicide and condom with vaginal diaphragm, vaginal sponge, or cervical cap)
 - * Both male (condom) and female (vaginal diaphragm, vaginal sponge or cervical cap) must use contraceptive devices together with spermicide.
- Sterilization surgery (vasectomy, bilateral tubal ligation, etc.)
- Complete abstinence: If preferred by the subject and matched with everyday lifestyle. [Periodic abstinence and coitus interruptus are not acknowledged as contraception.]

The Sponsor has the obligation to follow up on the results of pregnancy reported by female and male subjects during the clinical study. If it is not suspected that the investigational product interfered with the efficacy of appropriate contraception and contraceptives, the pregnancy itself is not considered an AE. In addition, voluntary induced abortion without complications, other than therapeutic abortion, is not considered an AE.

Within 24 hours of becoming aware of pregnancy, the Investigator shall prepare an initial pregnancy report and report it to the Sponsor. The Investigator shall track and document the process and results of all pregnancies even if the subject withdraws consent or terminates the clinical study. In addition, the investigator shall prepare a pregnancy result report and report it to the Sponsor within 24 hours of becoming aware of the results of any pregnancy (e.g., spontaneous labor, spontaneous abortion, etc.).

All SAEs (e.g., severe maternal complications, premature birth, therapeutic abortion, ectopic pregnancy, stillbirth, neonatal death, congenital anomaly, birth defects, etc.) that occurred from beginning of pregnancy to four weeks after childbirth shall be recorded in the SAE report and must be reported immediately to the PVA of DT&SanoMedics Co., Ltd., following the procedure in 7.4 Adverse Events.

8 Statistical Method

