- Patients with confirmed diagnosis of CMT1A by genetic testing;
- 3) Patients with mild-to-moderate severity assessed by Charcot-Marie-Tooth Neuropathy Score version 2 (CMTNS-v2) with a score > 2 and ≤ 20;
- 4) Individuals with lower limb muscle weakness with minimum dorsiflexion or
- 5) Individuals who voluntarily consent to participate in this study and sign the IRB-approved informed consent form after understanding a description on the characteristics of this clinical study prior to all screening tests;
- 6) Individuals who can comply with the requirements in the clinical study;
- 7) In case of females of childbearing potential, those who test negative in a urine or serum pregnancy test at screening;
- 8) Individuals who practice medically approved contraceptive methods* throughout the clinical study.

* Definition

- Drugs: Oral contraceptives, skin patches, or progestin formulations (implants or injections)
- Barrier methods: Condoms, diaphragms, intrauterine devices (IUDs), vaginal suppositories
- Abstinences: Complete abstinence (However, periodic abstinence (e.g., calendar method, ovulation method, and sympto-thermal method) and self-restraint are not considered as acceptable methods of contraception.)

Exclusion criteria

Subjects will be excluded from this clinical study if any one of the following criteria is met:

- 1) Patients with significant respiratory, circulatory, renal, gastrointestinal, hepatic, endocrine, hematologic, psychiatric disorders or other severe diseases, or alcohol or drug addiction who may develop safety issues or cause confusion in the interpretation of the clinical study results as determined by the principal investigator;
- 2) Patients with other neuromuscular diseases or neuropathy-inducing factors: Patients with chronic alcohol addiction, undergoing anticancer chemotherapy, or taking neurotoxic drugs;
- 3) Patients diagnosed with diabetes;
- 4) Patients diagnosed with inflammatory bowel disease;
- 5) Patients with a history of stroke or cerebral ischemic attack within 12 months prior to the screening date;
- 6) Patients with a history of coronary artery disease, such as myocardial infarction

and unstable angina pectoris within 12 months prior to the screening date;

- 7) Morbidly obese patients with body mass index (BMI) ≥ 37;

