5.3.2 Inclusion Criteria

Subjects enrolled in this clinical study must satisfy all of the following inclusion criteria:

- 1) Males or females \geq 19 years of age and \leq 65 years of age
- 2) Patients with confirmed diagnosis of CMT1A by genetic testing
- 3) Patients with mild-to-moderate severity assessed by Charcot-Marie-Tooth Neuropathy Score version 2 (CMTNS-v2) with a score > 2 and ≤ 20
- 4) Individuals with lower limb muscle weakness with minimum dorsiflexion or more
- 5) Individuals who voluntarily consented to participate in this study and signed the IRB-approved informed consent form after listening to a description on the characteristics of this clinical study prior to all screening tests
- 6) Individuals who can comply with the requirements in the clinical study
- In case of females of child-bearing potential, those who test negative in a urine or serum pregnancy test at screening
- 8) Individuals who practice medically approved contraceptive methods* throughout the clinical study

*Definitions

- · Drugs: Oral contraceptives, skin patches, or progestin formulations (implants or injections)
- · Barrier methods: Condoms, diaphragms, intrauterine devices (IUDs), vaginal suppositories
- Abstinences: Complete abstinence (However, periodic abstinence (e.g., calendar method, ovulation method, and sympto-thermal method) and self-restraint are not considered as acceptable methods of contraception.)

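### Criterion 8 and the 6.1.1 screening list accept a single barrier method, 7.4.7 accepts barriers only as condom plus female device plus spermicide, and no visible sentence says which rule governs

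*Protocol*

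**What the plan says.** Inclusion criterion 8, in the synopsis and 5.3.2, admits "Individuals who practice medically approved contraceptive methods* throughout the clinical study". Its definitions include the line "Barrier methods: Condoms, diaphragms, intrauterine devices (IUDs), vaginal suppositories", alongside hormonal drugs and complete abstinence. SAP 1.3.1 repeats the list. Protocol 6.1.1 gives the same list as the acceptable methods, under the urine HCG test for female subjects, and asks that the method be documented. None of these places asks for methods to be combined, mentions spermicide, or lists sterilization as a method. Section 6.1.1 mentions female sterilization only as a reason to skip the pregnancy test.

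Protocol 7.4.7 covers women of childbearing potential and men sexually active with such women. They "must practice appropriate contraception until the 7th visit (last visit, Day 270"); the sentence then adds a reference to the time after the last dose. The section presents its own list as the methods recognized in this study. Its barrier entry is "Double barrier method*(spermicide and condom with vaginal diaphragm, vaginal sponge, or cervical cap"), with the footnote "Both male (condom) and female (vaginal diaphragm, vaginal sponge or cervical cap) must use contraceptive devices together with spermicide". It also accepts hormonal methods, an intrauterine device or system, "Sterilization surgery (vasectomy, bilateral tubal ligation, etc".), and complete abstinence.

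Protocol 7.3 adds: "Women of childbearing potential who are administered with VM202 must be careful to avoid pregnancy".

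**The concern.** A site that follows 6.1.1 to the letter can record as acceptable a method that 7.4.7 rejects. The schedule of assessments places the pregnancy test at Visit 1 only. None is planned before the doses at Days 0, 14, 90 and 104, or in follow-up. After screening, the contraception instruction is therefore the main planned safeguard, and the protocol states it in two incompatible forms. What is at stake is which instruction subjects and site staff follow.

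A smaller issue is the coding of deviations. The sterilization methods accepted by 7.4.7 do not appear among the criterion 8 methods, so the eligibility status of a surgically sterilized subject has to be inferred.

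**Working it through.** The plan gives no figure to reproduce, so the check sets the texts side by side.

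| Method | Criterion 8 (and 6.1.1 for women) | 7.4.7 |
|---|---|---|
| Condom alone | listed | not accepted |
| Diaphragm alone | listed | not accepted |
| Vaginal suppository alone | listed | not accepted |
| IUD | listed (under barriers) | accepted |
| Condom + female device + spermicide | within the list, since it contains a condom | accepted |
| Hormonal | listed | accepted |
| Complete abstinence | listed | accepted, with a condition on preference and lifestyle |
| Vasectomy, tubal ligation | not listed | accepted |

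1. **Barrier items in conflict.** Criterion 8 names four: condom, diaphragm, IUD, suppository. Only the IUD stands alone under 7.4.7. In conflict: 4 − 1 = 3. Criterion 8 does not say in words that one barrier is enough. That follows from its listing methods one by one with no combination rule.

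2. **Time overlap.** Criterion 8 runs through the whole study. Section 7.4.7 ends at Visit 7. If its reference to the last dose is read narrowly, so that it starts only after the fourth dose (Day 104), the overlap is 270 − 104 = 166 days nominally. With the ±7-day windows at both visits, it runs from 263 − 111 = 152 to 277 − 97 = 180 days. If 7.4.7 is read as applying from Day 0, the nominal overlap is 270 days. On either reading both rules bind at the same time.

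3. **Does a stricter-rule-wins reading settle it?** Only for barriers. Section 7.4.7 is narrower on barriers and wider on sterilization, so neither list contains the other.

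4. **Population.** The 6.1.1 list sits under the female pregnancy test. For women the conflict arises from criterion 8 and 6.1.1 together; for men it arises from criterion 8 alone.

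5. **Number concerned.** The target is 12 subjects, and 5.7.1 says enrollment was complete at this version. The documents do not say how many rely on a single barrier or on sterilization, so the range is 0 to 12.

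**The case against.** For barrier users the rules are cumulative: anyone who follows 7.4.7 also meets criterion 8, because every 7.4.7 combination includes a condom. Section 7.4.7 is framed study-wide, and applying the stricter rule after enrollment is natural. That stands as the sensible resolution, but no sentence states it, and 6.1.1 gives site staff a list headed as acceptable. What subjects were told in the consent material cannot be seen here.

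Three stronger readings are tempting, and the documents do not support them.

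- **That the two rules fully coincide in time, so neither can be an entry rule.** Section 7.4.7 refers to the period after the last dose, so a partly post-dose reading is open. Only the overlap from the last dose to Day 270 is certain.
- **That a man relying on vasectomy is an inclusion violator who would lose dosing under 5.5.3 and his place in the PPS.** Criterion 8 omits all sterilization, so the same literal reading would fail a woman with tubal ligation, which is hardly intended. No such subject is shown, and it is not shown that anyone was still being dosed. PPS eligibility already goes to the data review meeting (Protocol 8.1.3, SAP 2.2.2 and 2.4). Losing one of at most 12 subjects (1/12 = 8.3%) from an auxiliary set would be arithmetic on an assumed event.
- **That a reproductive hazard has been shown.** Protocol 3.7 reports no germ cell transmission in nonclinical work.

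**Conclusion.** The contradiction is real in the current text and should be corrected. Two rules apply at once for at least the interval from last dose to Day 270, they disagree on three of four barrier items, and nothing visible ranks them. The sterilization gap is secondary and concerns both sexes.

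The size is modest. No sample size, alpha, endpoint or primary analysis depends on it, the Safety-set and ITT analyses are unaffected, and the PPS is auxiliary. The conclusion assumes that the criterion 8 methods may each be used alone, which its wording implies but does not say, and that no ranking sentence lies in text withheld from review. Completed enrollment does not remove the point: 7.4.7 binds to Day 270, and 5.7.2 still provides for subjects returning for visits after dosing.

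**What to change.** 1. State in 7.4.7 that, for the subjects it already covers, its methods apply from first dose through Day 270, with barriers accepted only as the double method with spermicide and sterilization accepted.
2. Make the list in 6.1.1 refer to 7.4.7.
3. Re-counsel any ongoing subject who relies on a single barrier.
4. Leave criterion 8 and its SAP copy as the historical entry rule, since enrollment has closed. The differing wording on abstinence need not be settled to cure this conflict.
5. Note for the data review meeting, in the Definition of Analysis Population document (SAP 2.4), that subjects who met the criterion 8 list or are surgically sterilized are not inclusion violations.

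The cost is a minor protocol amendment. Under Protocol section 16, amendments after study start are reserved for exceptional cases, need signed agreement of the sponsor and the principal investigator, and need MFDS or IRB approval where subject safety may be affected. Re-counselling concerns at most 12 subjects, possibly none.
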